General exercises are easily accessible, can be performed individually or in groups, and provide additional psychological and social benefits (**Miyamoto et al., 2019**). However, their direct biomechanical effect on the cervical musculature may be limited compared to specific exercises, which target known muscular imbalances such as reduced activation of deep stabilizers and over activity of superficial neck muscles (**Lauche et al., 2016; Ylinen et al., 2004**).

Despite the widespread use of both approaches, the current evidence is inconclusive regarding which is superior in improving pain and function. A recent systematic review and meta-analysis concluded that general exercises are **not superior** to specific exercises in reducing pain and disability in the short,

medium, or long term, but also highlighted the **low quality of available studies** and the need for high-quality randomized controlled trials (**Vieira Rosa et al., 2024**).

Statement of the Problem

Does the **addition of Body mind exercise, specific neck exercises or both to conventional physical therapy** reduce pain, disability, improve neck range of motion, isometric neck muscle strength and quality of life in patients with chronic mechanical neck pain?

Purpose of the Study

To investigate the effect of addition of body mind exercise, specific neck exercises or both to conventional physical therapy in patients with chronic mechanical neck pain on neck pain severity, functional disability, neck flexion range of motion, isometric neck muscle strength and quality of life.

Significance of the Study

Body mind exercises (mindful aerobic exercises) has been identified as a beneficial intervention for managing chronic mechanical neck pain. A recent systematic review and meta-analysis of randomized controlled trials found that body mind exercises (mindful aerobic exercises) significantly reduced pain intensity and disability in individuals with chronic mechanical neck pain, particularly when combined with other therapies such as strengthening exercises or acupuncture (**De Oliveira-Souza et al., 2024**).

Another systematic review focusing on patients with chronic mechanical neck pain highlighted that moderate-intensity aerobic exercises, performed three times per week for 30–45 minutes, led to improvements in pain, function, and disability levels (**Paraskevopoulos et al., 2023**). These findings underscore the importance

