Sample size was calculated using **G*Power software version 3.1.9.7**, referencing effect size data from a recent RCT comparing general and specific exercises in neck pain (**Vieira Rosa et al., 2024**). A priori power analysis for a repeated measures ANOVA (within-between interaction) was used with an effect size of 0.25, alpha level (α) = 0.05, and power ($1-\beta$) = 0.95. The estimated sample size required was **76 participants**, which was increased to account for potential dropouts as shown in (**Figure 1**). Thus, the total sample will include **80 patients**, randomly allocated into four equal groups ($n = 20$ per group):

- **Group A:** Conventional therapy.
- **Group B:** Conventional therapy + Body mind exercises (mindful aerobic exercise).
- **Group C:** Conventional therapy + specific neck exercises (cervical and scapular stabilization exercises)
- **Group D:** Conventional therapy + combined (body mind and specific) exercises

[figure not shown]

Figure 1 sample size calculation

Patients

A total of 80 patients (50-65 years old) with chronic mechanical neck pain will be recruited from outpatient orthopedic and physical therapy clinics. All participants will provide written informed consent prior to enrollment.

Inclusion Criteria (Daher et al., 2021)

- Adults aged between 50-65 years
- Diagnosis of chronic mechanical neck pain (pain duration ≥ 3 months)
- Pain intensity of at least 3/10 on the NPRS

Exclusion Criteria

- History of cervical surgery
- Specific neck conditions (fractures, neoplasm, infection)
- Pregnancy
- Severe cardiopulmonary disease or other systemic illness affecting participation

Randomization and Blinding

Participants will be randomly allocated into four groups using a computer-generated block randomization method. Allocation concealment will be ensured using sealed opaque envelopes. The **outcome assessor** will be blinded to group allocation.

Outcome Measures

All outcomes will be measured at **baseline (pre-intervention)** and after **6 weeks (post-intervention)**.

1. Pain Intensity

Measured using the **Arabic version of the Numeric Pain Rating Scale (NPRS)**, which has been validated for Arabic-speaking populations (**Alghadir et al., 2016**). Patients will be asked to rate their neck pain intensity on a scale from 0 (no pain) to 10 (worst possible pain).

2. Functional Disability

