6	Maintaining chin-tuck position plus unilateral and bilateral upper extremity with an external load of 500 ml full water bottle and reciprocal lower extremity movements in supine, prone, quadrupedal, and standing positions	15 s	12 times

Figure 3 *progression of cervical stabilization exercises adopted from Oz HE et al., (2024).*

Scapular stabilization exercises:

The Scapular stabilization exercises will be comprised of four exercise programs. The participants sat on the knees in 90° flexion position, and a Swiss ball was propped up between the chest and stomach. Looking from the side, the earlobe, acromion of scapula, and pelvis made a straight line (**Kang et al., 2021**).

A. Scapula retraction exercise: While retracting both the scapula, raise both the arms backward.

B. Scapula mobilization exercise: With thumbs up, raise both the arms sideways making a straight line with the shoulders.

C. Scapula dynamic stabilization exercise I: Raise one arm beside the ear and push out the other arm behind the back. Do the same for the opposite side.

D. Scapula dynamic stabilization exercise II: Raise both the arms beside the ears and then push them down bending and maintaining elbows at 90°. Raise both the arms beside the ears again and put them down.

Each exercise was performed with two sets of 15 reps, 10 sec per rep as shown in (Figure 4).

Figure 4 scapular stabilization exercises adopted from Kang et al., (2021).

Group D : Combined exercise group.

Group D will receive **conventional therapy in addition to mindful aerobic exercises, cervical and scapular stabilization.**

Statistical analysis:

Data will be analyzed using **SPSS version 27** (IBM Corp, Chicago, IL, USA). Descriptive statistics (mean \pm SD) will be reported for all variables. Normality of distribution will be assessed using the **Kolmogorov–Smirnov test**. **Within-group comparisons** (pre vs post) will be conducted using **paired t-tests**. **Between-group differences** will be analyzed using **one-way ANOVA** followed by **post hoc Tukey’s test**. The level of significance will be set at **p < 0.05**.

REFERENCES

- Alagingi NK. Chronic neck pain and postural rehabilitation: A literature review. *Journal of Bodywork and Movement Therapies*. 2022 Oct 1;32:201–6.
- Algarni, A. S., Ghorbel, S., & Jones, J. (2014). Validation of an Arabic version of the Neck Disability Index in patients with neck pain. *Spine*, 39(19), E1135–E1140.

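### The four equal arms form a 2x2 layout, but the only planned between-group analysis is one-way ANOVA with all-pairs Tukey: valid, yet it judges each added exercise on 20 against 20 and plans no interaction estimate

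*Protocol*

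**What the plan says.** The protocol's Purpose of the Study is "To investigate the effect of addition of body mind exercise, specific neck exercises or both to conventional physical therapy" in chronic mechanical neck pain. The Sample Size Calculation section has patients "randomly allocated into four equal groups ($n = 20$ per group"). The arms run from "Group A: Conventional therapy", through conventional therapy with one or the other exercise (Groups B and C), to "Group D: Conventional therapy + combined (body mind and specific) exercises".

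The Statistical analysis section fixes the between-group method: "Between-group differences will be analyzed using one-way ANOVA followed by" a post hoc Tukey test, at a significance level of 0.05. The only other inferential comparison is a paired t-test within each group. No main-effect contrast and no interaction is mentioned, and the protocol does not call the design factorial.

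**The concern.** Body mind exercise is absent in A and C and present in B and D. Specific exercise is absent in A and B and present in C and D. With equal cells, every patient carries information on both additions. A four-group Tukey analysis judges each addition from two arms only (B against A, C against A) and uses a critical value sized for six comparisons.

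Two things are at stake. One is precision: a moderate true benefit of adding either exercise would usually not reach significance in its Tukey comparison, in a trial that sets out in its Significance section to provide higher-quality evidence. The other is that the combined arm would be compared with each other arm, but nothing would say whether the two exercises add up or interfere when given together.

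**Working it through.** **Inputs.** From the protocol: four arms of 20, two-sided 5% level, baseline and 6-week measurements, and a Tukey test after one-way ANOVA. Assumed here: equal SD in all arms, differences in SD units, no dropout, no baseline adjustment. Pooled error df = 80 - 4 = 76. The protocol does not say whether the ANOVA is on 6-week values or on changes. The width ratios below are the same either way; only the SD behind them changes.

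**The plan's own figure.** The sizing reads "A priori power analysis for a repeated measures ANOVA (within-between interaction) was used", "with an effect size of 0.25, alpha level (α) = 0.05" and power "0.95. The estimated sample size required was 76 participants". With noncentrality f² x N x m/(1 - rho), m = 2 measurements, 3 and N - 4 df, and rho = 0.5 (assumed, as it is not in the readable text):
- N = 72: noncentrality 18, power 0.948
- N = 76: noncentrality 0.0625 x 76 x 2/0.5 = 19, power 0.959

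So 76 reproduces. With rho 0.3 the answer would be 104, and with rho 0.7 it would be 48. This figure sizes an overall group-by-time test. It does not give the precision for any one addition.

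**95% half-widths**
- Tukey pair, 20 against 20: 2.627 x sqrt(2/20) = 2.627 x 0.3162 = 0.831 SD
- Main effect, 40 against 40, unadjusted: 1.992 x sqrt(2/40) = 1.992 x 0.2236 = 0.445 SD
- Main effect, Bonferroni for two: 2.287 x 0.2236 = 0.511 SD
- Main effect, Bonferroni for two main effects plus interaction: 2.448 x 0.2236 = 0.547 SD
- Interaction (D - C - B + A), unadjusted: 1.992 x sqrt(4/20) = 0.891 SD

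**Ratio of the Tukey width to a main-effect width**
- Unadjusted: 0.831/0.445 = 1.87
- Bonferroni for two: 0.831/0.511 = 1.62
- Bonferroni for three: 0.831/0.547 = 1.52

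The 1.87 is sqrt(2) = 1.41 from pooling times 2.627/1.992 = 1.32 from the critical value.

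**Power with no interaction** (noncentral t, 76 df; the differences are illustrative)

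| True difference | Tukey pair | Main effect, Bonferroni for two | Main effect, unadjusted |
|---|---|---|---|
| 0.5 SD | 16% | 48% | 60% |
| 0.8 SD | 47% | 90% | 94% |

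**Power with a strong sub-additive interaction** (assumed). Let each exercise alone add 0.8 SD over A, and both together add no more than one. The effect of body mind exercise is then 0.8 SD without specific exercise and 0 with it, so the main effect is (0.8 + 0)/2 = 0.4 SD. Its power is 31% (Bonferroni for two) to 42% (unadjusted), below the Tukey pair's 47% for B against A.

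**The case against.** **The pairwise analysis fits the stated hypotheses.** Hypotheses 1 to 11 compare body mind, specific and combined exercise. The Significance section asks whether general or specific exercise is better, which is B against C. Tukey is valid for these, and B against C stays at 20 against 20 under any model. This stands. A reader might infer that one-way ANOVA with Tukey is an error, and the documents do not support that.

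**Group D was not justified by an interaction question.** A reader might infer that the combined arm exists to test whether the exercises add up or interfere. The Significance section instead cites a trial in which combined exercise did better than neck-specific exercise alone. That is D against C, which Tukey supplies. The lack of an interaction estimate is a missed use of the design, not a broken promise.

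**Main effects answer a somewhat different question.** The purpose concerns adding exercise to conventional therapy. A main effect averages that with the effect of adding it to conventional therapy plus the other exercise, and the two agree only without interaction. This stands too, and it is why the contrasts belong beside the pairwise comparisons and not in their place.

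**The widest ratio is not like for like.** It is tempting to say that the plan nearly doubles the interval. The 1.87 sets an interval adjusted for six comparisons against an unadjusted one. The fair range is 1.5 to 1.9, with 1.41 from pooling alone.

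**Group D's content is not fully settled.** Conventional therapy takes 40 minutes, the treadmill 30, and the scapular work about 20 (4 exercises x 2 sets x 15 repetitions x 10 s = 1,200 s). That reaches the upper end of the stated 60 to 90 minute session before any cervical work. The 2x2 reading needs D to receive both components as given in B and C, so these passages must be reconciled.

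**Further contrasts could sit in a separate analysis plan.** That is possible, but the protocol itself names the between-group method, and the point concerns that choice.

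**Conclusion.** The point holds as one of efficiency and completeness. The planned analysis is valid for pairwise questions. For the question of adding each exercise, its interval is 1.5 to 1.9 times as wide as a main-effect interval from the same 80 patients. It also plans no estimate of the interaction.

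The width comparison assumes equal arms and a common SD, and changes little with 19 per arm (0.853 against 0.457 SD, still 1.87). The power gain further assumes little or no interaction. The trial cannot verify that assumption: the interaction is estimated only to within about 0.89 SD, wider than either effect used in the power table. The gain is therefore conditional, and with strong sub-additivity it can reverse. That supports adding the factorial contrasts, but not replacing the pairwise comparisons with them.

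**What to change.** Amend the Statistical analysis section, before outcome data are compared by arm, as follows.

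1. Analyse the 6-week value of each outcome in a linear model with two factors (body mind yes/no, specific yes/no), their interaction, and the baseline value of that outcome as covariate.
2. Pre-specify two main-effect contrasts with a stated multiplicity adjustment: the mean of B and D minus the mean of A and C, and the mean of C and D minus the mean of A and B.
3. Report the interaction with its 95% confidence interval (half-width about 0.89 SD before baseline adjustment).
4. Keep all Tukey pairwise comparisons, including B vs A, C vs A, D vs A, B vs C and D vs C.
5. State that each main effect averages over the other exercise and equals the effect of adding it to conventional therapy alone only if there is no interaction. State also that a non-significant interaction test does not establish additivity.

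The cost is analysis wording: no new patients, visits or measurements, since the baseline value is already collected. The price in interpretation is that readers must take the main effects together with an imprecise interaction.

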of incorporating aerobic exercises into treatment plans for chronic mechanical neck pain to enhance patient outcomes.

Spinal stabilization exercises are popular for treating and preventing musculoskeletal neck disorders by the activation of deep muscles and controlling the over activity of surface muscles. (**Ibrahim Elnaggar et al., 2022**)

Ibrahim Elnaggar et al., (2022) compared the efficacy of cervical stabilization exercises and scapular stabilization exercises on neck pain severity, neck functional disability and neck mobility in treatment of patients with chronic mechanical neck pain. They found that cervical and scapular stabilization provided significant improvement in all the measured variables.

Incorporating both cervical and scapular stabilization exercises into rehabilitation programs can provide comprehensive benefits for individuals suffering from neck disorders. These exercises not only alleviate pain but also restore functional movement patterns, contributing to long-term musculoskeletal health (**Tian et al., 2025**).

This study addresses a crucial clinical question raised by a recent systematic review. Whether general or specific exercises are more beneficial in the treatment of chronic mechanical neck pain (**Vieira Rosa et al., 2024**). By using a randomized controlled trial design with well-defined outcome measures, this study aims to provide higher quality evidence to inform clinical guidelines and individualized treatment decisions (**Vieira Rosa et al., 2024**).

A secondary analysis of data from a randomized controlled trial reported that combining moderate general exercises and neck-specific exercise improved the work ability of patients with neck pain more than neck-specific exercise alone. The combination should be recommended in health promotion programs and will be investigated in the current study (**Daher A, 2021**).

Hypotheses

1. There will be no significant difference between body mind exercises, specific neck exercises or both on neck pain severity in patients with chronic mechanical neck pain.
2. There will be no significant difference between body mind exercises and specific neck exercises or both on functional disability in patients with chronic mechanical neck pain.
3. There will be no significant difference between body mind exercises and specific neck exercises or both on neck flexion range of motion in patients with chronic mechanical neck pain.

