4. There will be no significant difference between body mind exercises and specific neck exercises or both on neck extension range of motion in patients with chronic mechanical neck pain.
5. There will be no significant difference between body mind exercises and specific neck exercises or both on neck right lateral flexion range of motion in patients with chronic mechanical neck pain.
6. There will be no significant difference between body mind exercises and specific neck exercises or both on neck left lateral flexion range of motion in patients with chronic mechanical neck pain.
7. There will be no significant difference between body mind exercises and specific neck exercises or both on neck right rotation range of motion in patients with chronic mechanical neck pain.
8. There will be no significant difference between body mind exercises and specific neck exercises or both on neck left rotation range of motion in patients with chronic mechanical neck pain.
9. There will be no significant difference between body mind exercises and specific neck exercises or both on isometric neck flexor muscles strength in patients with chronic mechanical neck pain.

10. There will be no significant difference between body mind exercises and specific neck exercises or both on isometric neck extensor muscles strength in patients with chronic mechanical neck pain.
11. There will be no significant difference between body mind exercises and specific neck exercises or both on quality of life in patients with chronic mechanical neck pain.

Delimitations

The study will be delimited to

- Eighty patients
- Male and female patients diagnosed with chronic mechanical neck pain.
- The participants will be aged 50–65 years.
- Duration of illness will be greater than 3 months
- Intervention will last for 6 weeks, with 3 sessions per week.
- The interventions will include:
 - Conventional therapy: heat, massage, stretching exercises.
 - Body mind exercises (mindful walking).
 - Specific Exercises: Cervical and scapular stabilization exercises.
 - Combined Exercises: Mindful walking, cervical and scapular stabilization exercises.

Assumptions

- All participants will attend the scheduled sessions and comply with the prescribed home exercise program
- All participants will provide full effort during assessments and follow therapist instructions.
- No participants will receive additional treatment or medication during the study period.

Definition of Terms

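### Eleven hypotheses are each tested at 0.05 with no primary outcome named, so no single test of the trial's question has a controlled error rate

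*Protocol*

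**What the plan says.** The Hypotheses section runs from number 1, "There will be no significant difference between body mind exercises, specific neck exercises or both on neck pain severity", to number 11, "11. There will be no significant difference between body mind exercises and specific neck exercises or both on quality of life". Numbers 2 to 10 cover disability, six directions of neck motion, flexor strength and extensor strength.

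Outcome Measures lists five domains at one level, with pain first. None is called primary or secondary. Sample Size Calculation gives an effect size of 0.25, alpha 0.05 and power 0.95 for the within-between interaction of a repeated-measures ANOVA, and names no outcome.

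Statistical analysis then says: "Between-group differences will be analyzed using one-way ANOVA followed by post hoc Tukey’s test". It adds: "Within-group comparisons (pre vs post) will be conducted using paired t-tests". One level governs all of this: "The level of significance will be set at p < 0.05". No order of testing or adjustment across outcomes is given.

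**The concern.** The Statement of the Problem poses one question, whether adding these exercises helps, and the Significance section wants the answer to inform guidelines. That question is put to eleven tests of equal standing, each with its own 5% error. Six of the eleven are directions of a single measurement, so more than half of the chances of a significant result lie in range of motion. The list of outcomes also varies: the Purpose names only flexion among the motion outcomes, while the hypotheses name six directions.

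At stake is how a mixed result would be read. If one or two of the eleven tests are significant, the protocol does not say which of them answers the question, and the power statement cannot help because it belongs to no outcome.

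**Working it through.** **Inputs from the protocol.** Four groups of 20 (80 in all); required N of 76; two time points; f = 0.25; alpha 0.05; power 0.95; eleven hypotheses; one-way ANOVA with Tukey's test. **Assumed, because the text does not state them:** a correlation of 0.5 between the two time points and a sphericity factor of 1 for the sample size; a range of correlations between outcomes for the error rate.

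**1. The protocol's own figure.** For the interaction, λ = f² × N × m / (1 − ρ), with m = 2 time points, 3 and N − 4 degrees of freedom. At N = 76, λ = 0.0625 × 76 × 2 / 0.5 = 19, and power is 0.959. The smallest N with power of at least 0.95 is 73, which becomes 76 in four equal groups. At N = 80, power is 0.968. The stated 76 is reproduced.

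**2. What Tukey's test covers.** Four groups give 4 × 3 / 2 = 6 pairs. Tukey's test holds 5% over those six pairs for one outcome and does nothing across the eleven.

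**3. Error across the eleven overall ANOVAs, all nulls true.**
- Independent outcomes: 1 − 0.95^11 = 0.431.
- Bound under any dependence: 11 × 0.05 = 0.55.
- Equally correlated normal outcomes, 4 × 20 patients, 40,000 simulated trials:

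| Correlation between outcomes | Chance of at least one p < 0.05 |
|---|---|
| 0 | 0.431 |
| 0.3 | 0.381 |
| 0.5 | 0.320 |
| 0.7 | 0.235 |
| 0.9 | 0.143 |

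The paired t-tests are left out of these figures (11 outcomes × 4 groups = 44 if all are run). So is any separate scoring of quality-of-life scales.

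**4. Which test the power statement fits.** With two time points, the interaction test is the same as a one-way ANOVA of change from baseline. At N = 80 the protocol's inputs give λ = 0.0625 × 80 × 2 / 0.5 = 20. On the change scale this is an f of √(20/80) = 0.5. If 0.25 is instead read as the f of a one-way ANOVA of 6-week scores, λ = 0.0625 × 80 = 5 and power is 0.42. The two uses of 0.25 are not the same effect, so the stated power cannot simply be moved to an ANOVA of 6-week scores.

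**5. What adjusting all eleven would cost.** Bonferroni gives 0.05 / 11 = 0.00455 per hypothesis. Under the model in step 1, power falls to 0.79 at N = 76 and 0.82 at N = 80, and N = 108 would be needed for 0.95.

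**The case against.** The best reply is that the eleven hypotheses are separate statements about separate outcomes, each correctly tested at 5%. Family-wise error concerns a claim that the treatment works if any outcome is significant. A reader might infer such a rule, but the protocol nowhere states one. That part of the reply stands: 43% is not the error rate of a decision rule in the document. It does not restore a controlled test, because the trial asks one overall question and names no outcome that answers it.

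A reader might also take 43% as a ceiling. It is the value under independence. The bound under any dependence is 55%, and with positively related outcomes, which is the plausible case here, the rate is lower.

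Nor can it be shown that the headline outcome would be picked after the data are seen. The protocol commits to registration before enrolment, and the registry entry is not at hand.

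Finally, an adjustment procedure is often left to the SAP, and its absence here is not the point. The point is what the protocol itself fixes: a flat 0.05 over eleven unranked hypotheses, and a sample size attached to none of them.

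**Conclusion.** The concern holds in this form: in the text at hand no primary outcome is named, the sample size is tied to no outcome, and eleven hypotheses are each tested at 0.05 without control across outcomes. If all eleven nulls are true, at least one overall ANOVA is significant in about 43% of trials with independent outcomes, and in roughly 24% to 38% at correlations of 0.7 to 0.3. That correlation range is an assumption; the protocol gives no correlations. Even at 0.9 the rate is 14%, nearly three times the nominal 5%. This should be settled before outcome data are seen, because a choice made later would carry little weight.

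**What to change.** 1. Name one primary outcome in Hypotheses, Outcome Measures and Sample Size Calculation. Pain on the NPRS at 6 weeks is one candidate, being already outcome 1 and hypothesis 1; another choice is open to the sponsor if made in advance. If pain is chosen, reconcile Definition of Terms, which allows either a VAS or the NPRS.
2. Test it at two-sided 0.05 with a model that matches the sample-size calculation: the group-by-time interaction, equivalently a one-way ANOVA of change from baseline, or a baseline-adjusted ANCOVA. Do not attach the 0.95 power to a one-way ANOVA of 6-week scores at f = 0.25. State the correlation assumed between time points.
3. Make the other ten outcomes secondary. Either apply Holm's procedure to them only if the primary is significant, or report estimates with 95% confidence intervals and no confirmatory claim. The gate matters: an ungated primary at 0.05 beside a Holm family at 0.05 leaves 1 − 0.95² = 0.0975 overall under independence.

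The cost is a few sentences, matched in the registry entry. N is unchanged, whereas Bonferroni over all eleven would need 108 patients for the same power. The downside is that the secondary outcomes lose confirmatory status or face a stricter threshold.
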